## Secondary Endpoints:

- Score on the ease of airway clearance pictorial analogue scale from all participants.
- Participants' perception of treatment.

#### 4. PARTICIPANT ENTRY

### 4.1 PRE-REGISTRATION EVALUATIONS

[This section does not apply]

#### 4.2 INCLUSION CRITERIA

[Children and young people under 18 years old with Neuromuscular disease or with Cerebral Palsy treated with nebulised Hypertonic Saline for at least 12 months and their parents or legal guardians.]

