#### **ELIGIBILITY**

Inclusion cirteria: Children and young people with Neuromuscular disease or Cerebral Palsy who have their care at the Royal Brompton Hospital and are on treatment with nebulised Hypertonic Saline for at least 12 months.

Exclusion criteria: Children or young people also diagnosed with Cystic Fibrosis.

**DURATION** 6 months

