## Secondary Objectives:

- Assess the effect of the treatment with nebulised hypertonic saline in children and young people with Neuromuscular disease or Cerebral Palsy on the number of courses of antibiotic prescribed compared to year before starting treatment.
- Determine whether the use of nebulised Hypertonic Saline in children and young people with Neuromuscular Disease or Cerebral Palsy reduces the frequency of hospitalisations due to respiratory exacerbations compared to year before commencing treatment.
- Explore the impact of the treatment with hypertonic saline on nocturnal oxygenation and ventilation in children and young people with Neuromuscular disease or with Cerebral Palsy.
- Evaluate whether the treatment with nebulised hypertonic saline in children and young people with neuromuscular disease or cerebral palsy improves the ease of airway clearance.
- In the subgroup of participants with neuromuscular disease who can perform spirometry, assess whether the use of Hypertonic Saline decreases rate of decline of pulmonary function compared to year before commencing treatment.
- Explore how parents of children and young people with Neuromuscular disease or with Cerebral Palsy perceive the treatment with nebulised hypertonic saline compared to previous management.

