# 3. STUDY DESIGN

[Chart review of children and young people with Neuromuscular disease or with Cerebral Palsy who are cared for in the Royal Brompton Hospital and that have been treated with nebulised hypertonic saline for at least 12 months. Children and young people who are also diagnosed with Cystic Fibrosis will be excluded.

Parents or legal guardians will be asked to complete two questionnaires to further complement data from hospital records.

Participants between 10 and 18 years old will be asked to complete one questionnaire to complement hospital records.]

[Duration: 6 months.]

[We aim to review all charts of participants recruited that meet criteria between December 2011 and May 2018. We aim to recruit 40 participants from each group, including children, young people, and parents or legal guardians, as this will be a pilot study. Only participants recruited will have their charts reviewed]

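### Eligibility secures 12 months on hypertonic saline but no observed year before it, and the before/after count analyses make no allowance for unequal observed time

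*Combined protocol and SAP*

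**What the plan says.** Section 4.2 sets the entry rule: children under 18, with no lower age limit, "treated with nebulised Hypertonic Saline for at least 12 months". The Eligibility paragraph of the Study Summary adds care at the hospital and says that they "are on treatment with nebulised Hypertonic Saline for at least 12 months". Neither asks for any time under observation before treatment began.

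The secondary objectives in section 2 take the preceding year as comparator. One concerns the "number of courses of antibiotic prescribed compared to year before starting treatment"; another asks whether treatment "reduces the frequency of hospitalisations due to respiratory exacerbations compared to year before commencing treatment". Section 3.1 lists both counts among the primary endpoints.

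Section 3 gives the only calendar dates: "We aim to review all charts of participants recruited that meet criteria between December 2011 and May 2018". It also says that parent questionnaires will supplement the hospital records. The parent questionnaire in the appendices asks for oral and intravenous antibiotic courses, and for visits to a doctor, in the 12 months before and the 12 months after starting. Parents who do not remember leave the item blank.

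Section 6 plans univariate chi-square analyses of antibiotic courses and of hospitalisations. It gives no annualised rate, no offset for observed time, no rule for an incomplete year on either side, and no rule for combining chart and questionnaire.

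**The concern.** A before/after comparison of counts needs the same observed time on both sides of the start, or an adjustment for the difference. The entry rule secures a year of treatment after the start and leaves the comparator year to chance. A child who started at eight months of age has not lived a full before-year. A child who started soon after referral may have spent that year under another hospital, with its events in records that the study does not hold.

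If months without a record are in effect counted as months without events, the before-count is too low and the after/before ratio too high. A real reduction would then look smaller, and no effect could look like harm. Two primary endpoints are exposed to this.

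**Working it through.** The plan gives no figure for completeness of the before-year, no event rates and no distribution of start dates. The recruitment target of 40 per group is justified only as a pilot. There is thus no figure of the plan's own to reproduce, and the check is date arithmetic under stated assumptions.

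**Inputs from the documents.** Comparison: 12 months before against 12 months after starting (section 2; the parent questionnaire uses the same two periods). Minimum time on treatment: 12 months (section 4.2). Dates: December 2011 to May 2018 (section 3), which is 1 + 72 + 5 = 78 months.

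**Assumptions not in the documents.** Starts are uniform over the stated range, the event rate is constant, and unobserved months add no events to an unadjusted count.

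**Formula.** Apparent ratio = true ratio × (after-time observed ÷ before-time observed).

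**Main case, if the dates bound extraction.**

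- Starts that leave 12 months by the end of May 2018 run from December 2011 to May 2017: 78 − 12 = 66 months.
- Starts in the first 12 of these have a cut before-year: 12/66 = 18.2%. If a group holds 40 children, that is 12/66 × 40 = 7.3, about 7.
- Those children lose half a year on average, so before-time observed is (12 × 0.5 + 54)/66 = 60/66 = 90.9%.
- After-time observed is 100%. With no effect the ratio is 66/60 = 1.10; a true 0.80 appears as 0.80 × 1.10 = 0.88, and a true 0.70 as 0.77.

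**Range over start dates.**

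| Case | Before-years cut | After-years cut | After-time ÷ before-time = ratio with no effect | True 0.80 appears as |
|---|---|---|---|---|
| Dates only define when criteria are met | 0% | 0% | 1.00 | 0.80 |
| Extraction bounded, starts Dec 2012 to May 2017 | 0% | 0% | 1.00 | 0.80 |
| Extraction bounded, starts Dec 2011 to May 2017 | 12/66 = 18% | 0% | 66/60 = 1.10 | 0.88 |
| Extraction bounded, starts Dec 2011 to Nov 2014 | 12/36 = 33% | 0% | 36/30 = 1.20 | 0.96 |
| Extraction bounded, starts Dec 2010 to May 2017 | 24/78 = 31% | 12/78 = 15% | 72/60 = 1.20 | 0.96 |

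In the last row, starts before December 2011 lose after-time as well as before-time.

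**Incomplete records for other reasons** (infancy, late referral, care elsewhere). If a share f of before-time is unrecorded and scored as zero, and after-time is complete, the ratio with no effect is 1/(1 − f): 1.05 for 5%, 1.11 for 10% and 1.25 for 20%. If a share g of after-time is also lost, it is (1 − g)/(1 − f). Equal losses cancel; a 10% loss of after-time alone gives 0.90, which favours treatment.

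These ratios describe a comparison of mean counts. They show how far the data going into the analysis would be distorted; they are not the output of the chi-square test in section 6.

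**The case against.** Three arguments against the point carry weight.

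First, a reader might infer that the calendar window definitely cuts off before-years. The documents do not establish this. In section 3 the dates attach most naturally to participants meeting the criteria, and section 2 sets the comparison year relative to each child's start. On that reading the window removes nothing. Even on the other reading, it cuts before-years only if some children started before December 2012, and no start dates are given.

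Second, a reader might infer that before-counts must be understated and that the bias is one-sided. Nothing says that unobserved months score zero. If such children are left missing, excluded or completed from the questionnaire, the problem becomes missing data or recall error instead of a fixed undercount. Nor does the entry rule guarantee a year of records after starting: it guarantees a year of treatment, which may have begun elsewhere or before December 2011.

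Third, the chart is not the only source. The parent questionnaire covers antibiotic courses and doctor visits on both sides without restriction to this hospital, and the hospitalisation endpoint refers to a NHANES questionnaire. This is a real mitigation, but a partial one. The before-year may lie several years back and is recalled, blanks are allowed, the parent items shown ask about doctor visits and not admissions, and no rule says which source prevails.

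What remains is the gap itself. The plan admits children whose comparator year is partly or wholly unobserved and does not say how they are analysed. That does not depend on how the dates are read.

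**Conclusion.** The point holds as a gap in design and analysis, not as a demonstrated bias of known direction. Eligibility is silent on the period before treatment, two primary count endpoints depend on that period, and section 6 has no means of handling unequal observed time.

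The window alone contributes between nothing (0% cut, ratio 1.00) and, with uniform starts from December 2011 to May 2017 and dates that bound extraction, 18% of before-years cut and a ratio of about 1.10. Starts concentrated earlier, or reaching back to December 2010, give 1.20. Each figure above 1.00 also needs unobserved months to be scored as event-free.

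An undercount of before-events taken alone would hide benefit. Incomplete after-years act the other way. So would regression to the mean if treatment tended to start after a bad year. The net direction for the study cannot be stated from the documents. The change is still worth making, because it is cheap and removes a possible bias from two primary endpoints.

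**What to change.** **Section 3.** Define extraction relative to each child, from 12 months before to 12 months after first use of hypertonic saline, and not by calendar dates. If December 2011 to May 2018 is kept, say that it defines only when criteria are met. Record for each child the number of observed months on each side, meaning months in which an event would have reached the study's sources.

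**Section 6.** Compare paired before/after rates of antibiotic courses and of hospitalisations, with the log of observed months as offset, and never count unobserved months as zero. Base the main before/after analysis on children with a full 12-month record on both sides, from the chart plus outside records or questionnaire where available. Add children with shorter records in a sensitivity analysis; this is where the offset does its work. State which source prevails when chart and questionnaire disagree, and that a blank answer is missing and not zero. An offset cannot recover events recorded elsewhere if the month is wrongly classed as observed, so the definition of an observed month matters.

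**Cost.** Wording in sections 3 and 6, and two extra data items per child. The main analysis set becomes smaller: none to about 18% fewer on the window alone (the upper figure if earlier records cannot be retrieved and starts are uniform as above), possibly more because of late referrals. It is also selected somewhat toward children with longer prior care at the hospital, which the sensitivity analysis addresses. No child leaves the study.

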#### 4.3 EXCLUSION CRITERIA

[Children or young people who are also diagnosed with Cystic Fibrosis, as the effectiveness of nebulised Hypertonic Saline have already been studied extensively in this group.]

## 4.4 WITHDRAWAL CRITERIA

[This section does not apply.]

# ASSESSMENT AND FOLLOW-UP

[This section does not apply]

## 6. STATISTICS AND DATA ANALYSIS

[Sample Size:

We aim to recruit 40 participants for each group, including children and young people and their parents or legal guardians, as this is a pilot study.

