Children with Neuromuscular disease show a decline of Forced Vital Capacity (FVC), which is steeper at younger ages (13). This is especially important because the age at which FVC reaches 1 Lt and the rate of decline of FVC are variables that can predict mortality (14).

Pneumonia, respiratory exacerbations and failure are one of the most important causes of emergency admissions, hospitalisations and death in children with neuromuscular diseases and cerebral palsy (15-18). Physical health and the number of days spent outside home or hospitalised are important domains of life and predictor of Health-Related Quality of Life in children with Neuromuscular disease and children with Cerebral Palsy (19,20). In this context, it is of importance to research how to therapeutically aid airway clearance, decrease respiratory exacerbations and reduce the pulmonary function rate of decline.

Hypertonic Saline is a solution of salt water used as a nebulized medication in many conditions. Its clinical benefits include mucus clearance, microbiological diagnosis, improvement of lung function, decrease in respiratory exacerbations, cough triggering and improvement of quality of life (21). It has mucolytic and expectorant effect, reduces biofilm formation by Pseudomonas Aeruginosa and increases antioxidative thiols in the airway liquid (22).

Retrospective studies and clinical trials have shown that inhaled Hypertonic Saline is well tolerated, reduces pulmonary exacerbations, improves lung function and Lung Clearance Index, reduces absenteeism, improves Health Related Quality of Life in patients with Cystic Fibrosis independent of rhDNase treatment (23-26), and has anti-inflammatory effect in sputum decreasing

IL-8 (27). In asthmatic and healthy subjects, inhaled Hypertonic Saline have shown to enhance mucociliary clearance (28). To date, studies investigating Hypertonic Saline in bronchiectasis have produced conflicting results (29).

This study aims to assess the effectiveness of the use of nebulised Hypertonic Saline in respiratory outcomes in children and young people with Neuromuscular disease or with Cerebral Palsy.

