#### 1.2 RATIONALE FOR CURRENT STUDY

[To our knowledge, there is currently no available data concerning the use of nebulised Hypertonic Saline in the management of children and young people with Neuromuscular Disease or with Cerebral Palsy. This study aims to assess whether the use of nebulised Hypertonic Saline in children and young people with Neuromuscular disease or Cerebral Palsy is effective in the management and prevention of respiratory-related complications.

Hypothesis: Nebulised Hypertonic Saline in children and young people with Neuromuscular disease or Cerebral Palsy decreases respiratory-related complications.]

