## 2. STUDY OBJECTIVES

[Primary Objective: To explore whether treatment with 3% and 7% Nebulised Hypertonic Saline in children and young people with Neuromuscular Disease or Cerebral Palsy decreases respiratory-related complications.

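### The size rests on pilot status alone, yet before/after effectiveness questions are to be answered by tests, with no within-child estimate or confidence interval planned

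*Combined protocol and SAP*

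**What the plan says.** **Size.** Section 6 (Sample Size) states "We aim to recruit 40 participants for each group". The number takes in parents and guardians as well as patients, and pilot status is the only reason offered. Section 3 repeats it: "We aim to recruit 40 participants from each group, including children, young people, and parents or legal guardians, as this will be a pilot study". Neither place gives a significance level, power, effect size, event rate, standard deviation or target precision. Neither says what the groups are or how many of the 40 are children.

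**Questions asked.** The primary objective (section 2) is exploratory: "To explore whether treatment with 3% and 7% Nebulised Hypertonic Saline" decreases complications. Elsewhere the wording is about effectiveness. Section 1.1 ends with "This study aims to assess the effectiveness of the use of nebulised Hypertonic Saline in respiratory outcomes". Section 1.2 states a directional hypothesis: "Nebulised Hypertonic Saline in children and young people with Neuromuscular disease or Cerebral Palsy decreases respiratory-related complications". One secondary objective is to "Determine whether the use of nebulised Hypertonic Saline in children and young people with Neuromuscular Disease or Cerebral Palsy reduces the frequency of hospitalisations" for respiratory exacerbations, relative to the year before treatment.

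**Analyses.** For the primary endpoints, section 6 names:
- chi-squared analysis for antibiotic courses and for hospitalisations;
- a Student t test, year before against year after, for nocturnal outcomes;
- independent t and Mann-Whitney tests for rate of lung function decline;
- a Cox model described as a test of differences.

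The secondary endpoints get an unspecified univariate analysis. No effect measure, confidence interval, significance level or rule for reading a non-significant result is given.

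**The concern.** Calling the study a pilot can excuse the absence of a power calculation if the study then estimates something and reports how precisely. Here the analysis list consists of tests and a model for testing, while several statements of purpose ask whether the treatment works. A bare P value above 0.05 from a small study does not separate no effect from a useful effect measured imprecisely, and the plan has no output that would show the difference.

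The tests also do not match the comparison. The objectives compare the same child's year before and year after starting saline. A chi-squared test across the two periods and an independent t or Mann-Whitney test treat the two years as separate samples. A chi-squared test also reduces event counts to categories. The section does not say whether the Student t test is paired. What is at stake is whether the study's data, in a population for which section 1.2 says none exist, are reported as an estimate with its uncertainty or only as significant or not.

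**Working it through.** **1. The plan's own figure.** The 40 per group cannot be reproduced, because no input to a power or precision calculation is stated. The check is therefore what such a size can support.

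**2. Inputs.** From the documents: 40 participants per group, and a comparison of the year before with the year after. All of the following are assumptions, because the documents give no rates or effects:
- true rate ratio 0.75;
- 1 or 3 events per child-year before treatment (λ);
- variance equal to Poisson (φ = 1) or twice Poisson (φ = 2);
- two-sided 5% level;
- 20, 40 or 80 children (n). Twenty applies if parents take up half of one group of 40; 80 applies if there are two groups each with 40 children.

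**3. Formulas.**
- SE(log RR) = √{φ[1/(nλ) + 1/(0.75nλ)]}
- Power ≈ Φ(z − 1.96) + Φ(−z − 1.96), with z = |ln 0.75|/SE = 0.2877/SE
- Expected 95% interval = 0.75 × exp(±1.96 SE)

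The formula adds the variances of the two periods as if independent. Stable differences between children cancel in a within-child ratio, so φ = 1 applies if those are the only extra variation. φ = 2 stands for additional year-to-year variation within a child.

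**4. Worked case, 40 children.**
- λ = 3, φ = 2: SE = √{2(1/120 + 1/90)} = 0.197; z = 1.46; power 31%; interval 0.51 to 1.10.
- λ = 3, φ = 1: SE = 0.139; z = 2.06; power 54%; interval 0.57 to 0.99.
- λ = 1, φ = 2: SE = √{2(1/40 + 1/30)} = 0.342; z = 0.84; power 13%; interval 0.38 to 1.46.
- λ = 1, φ = 1: SE = 0.242; z = 1.19; power 22%; interval 0.47 to 1.20.

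**5. All sizes: power, φ = 2 to φ = 1.**

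| Children | 1 event/child-year | 3 events/child-year |
|---|---|---|
| 20 | 9–13% | 18–31% |
| 40 | 13–22% | 31–54% |
| 80 | 22–39% | 54–83% |

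**6. Continuous outcomes.** For a paired change, the 95% half-width is t(0.975, n−1)/√n standard deviations of the change: 2.093/√20 = 0.47, 2.023/√40 = 0.32 and 1.990/√80 = 0.22. From the noncentral t distribution, the change detectable with 80% power is 0.66, 0.45 and 0.32 SD. Lung function decline is assessed only in participants with neuromuscular disease who can perform spirometry, so its number will be smaller than the number of children recruited.

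**7. A second set of assumptions.** With a rate ratio of 0.7, no overdispersion and an exact conditional test, 40 children give power of 13%, 27% and 51% at 0.5, 1 and 2 events per child-year. The conclusion does not hinge on the choice of 0.75.

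**The case against.** **The purpose is mostly exploratory.** This stands in part. The primary objective and two of the secondary objectives begin with *explore*, and *determine whether* occurs in one secondary objective only. A reader might infer that the objectives as a whole are confirmatory. They are not. The conflict lies in that one objective and in the background and rationale.

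**The documents never say that a null result means no effect.** This stands. A reader might infer that the plan would conclude that saline does not work whenever P>0.05. There is no significance level, decision rule or interpretation rule from which that follows. The supportable statement is that nothing in the plan prevents such a reading.

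**The number of children may not be about 40.** This stands. The groups could be the two diagnoses, the two saline strengths, or children and parents. With 80 children and 3 events per child-year, power is 54–83%, so it cannot be said that a real 25% reduction would usually be missed. For frequent events that already fails at 40 children with Poisson variation (54%).

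**The data would still serve a later trial.** This stands. A reader might infer that nothing would remain with which to size one. In fact counts before and after are collected for each child, and event rates and dispersion can be computed from them. The documents do not mention a later trial.

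**A false negative is not the main risk.** Only children treated for at least 12 months are eligible and there is no control group, which can favour apparent benefit. This is a fair limit on the point, but no reason to omit estimates and intervals.

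**A Cox model can give hazard ratios.** True, but section 6 does not say that they will be reported.

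**Conclusion.** The point holds in a limited form. The size has no basis beyond "as this is a pilot study", and the groups and number of children are undefined. Some statements of purpose ask whether saline is effective, while the primary analyses are tests with no planned estimate or interval, several of them not suited to a within-child comparison.

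Under the assumed inputs, power for a 25% reduction is at most 39% for events occurring about once per child-year, even with 80 children. For events occurring three times a year it runs from 18% to 83%. A non-significant result would therefore often, though not always, be compatible with a worthwhile reduction. These figures rest on assumed rates, effect and dispersion, on the two periods being treated as independent, and on no bias. They illustrate what the size can support and are not properties of the plan itself.

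The part that carries the point is the missing within-child estimate with its interval. This is worth correcting before analysis.

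**What to change.** In section 6, in place of the unpaired tests, make the main result for each primary endpoint a within-child estimate with a 95% confidence interval:
- antibiotic courses and hospitalisations: rate ratio, year after to year before;
- nocturnal outcomes: paired mean change (for snoring, if recorded as present or absent, the paired change in proportion);
- rate of lung function decline: paired mean change in rate, in those with spirometry.

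State that P>0.05 will not be read as absence of effect. In sections 3 and 6, define the groups and give the number of children separately from parents or guardians. In section 2, align the hospitalisation objective with the exploratory primary objective by replacing *determine whether* with *estimate*. Any precision statement added should be labelled as resting on assumed rates and shown as a range.

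**Cost.** Wording and a little more analysis, on data already being collected and with no extra participants. The claim becomes weaker than the current text allows. An interval does not remove the bias of an uncontrolled before/after comparison, and the report should say so.
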